### **13.2. Criteria for Termination of the Trial**

The trial will be terminated upon completion of the final visit by the last active participant or unless any of the conditions of Section 7.4 are met. An active participant is one who is enrolled in the study and has not been discontinued.

### **13.3. Accountability of Data**

Individual data points that are missing will be excluded from analysis involving only those specific variables. A participant's complete visit data will not be excluded if some of the observations are missing. Data from unscheduled visits will be used only for adverse response analysis. Inclusion of outliers in the analysis will be based on the magnitude of change in test statistic with and without the outliers. Outliers will preferably be retained unless there is significant change in test results.

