## 13. STATISTICS

### 13.1. Description

Data stored in relational databases will be imported into SPSS software for statistical purposes. Statistical analysis will initially be reported in Excel. The study may employ at least one interim analysis. Data will be investigated for quality using range checks and frequency distribution. Underlying distributions of variables will be tested. In general, variables measured on an interval scale with a sufficiently large sample size will be considered to follow a normal distribution. Details of statistical analysis are described in Section 13.1.3.

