#### 13.1.3. Analysis

Participants who have commenced the study treatment will be included in the analysis dataset. Reasons and frequency distribution of participants discontinued at Baseline will be reported. The analysis of efficacy variables such as subjective ratings will employ only scheduled and evaluable visits.

The analysis of safety variables such as adverse responses will include all visits, including all unscheduled visits.

Data will be summarised as means  $\pm$  standard deviations for variables measured on an interval scale and median  $\pm$  inter-quartile range for ordinal variables. Statistical tests will be employed to determine significant differences between between visits and  $p \leq 0.05$  will be considered statistically significant. Multiple comparisons will be adjusted using Bonferroni's correction. Commonly used tests of significance at each visit may include paired t-tests and group t-test for parametric data and Wilcoxon sign rank test and rank sum test for non-parametric data or repeated measures Analysis of Variance (ANOVA) for parametric data to determine differences between within-subject factors. Ranked variables will be analysed non-parametrically using Friedman's analysis of variance or Wilcoxon Signed Rank test to determine differences. Paired categorical variables will be compared using McNemar's test and grouped categorical variables will be analysed using Chi-Square tests.

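### If the repeated-measures ANOVA or Friedman's test listed in section 13.1.3 is used across the three visits, participants who missed only the 1-month visit are deleted and their observed 3-month scores are discarded

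*Combined protocol and SAP*

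**What the plan says.** Section 13.3 (Accountability of Data) has two relevant sentences. The first works at the level of the variable: "Individual data points that are missing will be excluded from analysis involving only those specific variables". The second works at the level of the visit: "A participant's complete visit data will not be excluded if some of the observations are missing". Neither says what happens when a whole visit is missed.

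Section 13.1.3 (Analysis) gives a menu of tests and names none as primary. It opens permissively: "Commonly used tests of significance at each visit may include paired t-tests and group t-test for parametric data". Signed-rank and rank-sum tests follow for non-parametric data, and then the longitudinal alternative: "or repeated measures Analysis of Variance (ANOVA) for parametric data to determine differences between within-subject factors". For ordinal scores it says: "Ranked variables will be analysed non-parametrically using Friedman's analysis of variance or Wilcoxon Signed Rank test to determine differences". No mixed model, imputation or deletion rule appears.

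Section 6.1.4 sets three scheduled visits: baseline, 1 month and 3 months. Section 7.1.1 makes a baseline OSDI score a condition of entry. Section 13.1 names the software: "Data stored in relational databases will be imported into SPSS software for statistical purposes".

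**The concern.** Classical repeated-measures ANOVA and Friedman's test work on complete rows: each participant needs a value at every visit in the analysis. Baseline OSDI is needed for entry, so the pattern that matters is a participant with baseline and 3-month scores but no 1-month score. Under either test that participant drops out, and a 3-month score already in hand goes unused. In the same way, someone who leaves after the 1-month visit contributes nothing to these tests, although the 1-month score was observed.

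Two things are at stake. The first is precision, because the sample size has almost no slack once its own 10% drop-out is taken off. The second is whom the result describes: a complete-row analysis covers only people who attended every visit. If missing the 1-month visit is related to symptoms, the retained group differs from those with a 3-month score. Both effects would come from the choice of analysis, since the 3-month data exist.

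**Working it through.** **Inputs from the documents.** OSDI difference 10, SD 20, two-sided alpha 0.05, power 80%, 69 per group including 10% drop-out (section 13.1.1); three visits (section 6.1.4).

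**Assumed input.** The share x of participants with a 3-month score who missed the 1-month visit. The documents give no figure, so a range up to 20% is shown.

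**1. Reproduce the plan's sample size.** n per arm = 2 × (1.960 + 0.842)² × 20² / 10² = 62.8, or 63 after rounding up. Multiplying by 1.1 gives 62.8 × 1.1 = 69.1, that is 69 per arm and 138 in total. Dividing by 0.9 gives 63/0.9 = 70 per arm and 140 in total, 2 more than stated. The plan's figure reproduces.

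**2. Check the mechanics.** A small artificial data set (20 participants, three visits, one middle-visit value missing) was analysed both ways. Classical repeated-measures ANOVA rejected the data as unbalanced. Friedman's test returned no result until the incomplete participant was removed.

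**3. Size of the loss.** After 10% drop-out, 69 × 0.9 = 62.1 per arm have a 3-month score. Requiring all three visits leaves 62.1 × (1 − x). Power for the two-group comparison behind the sample size is Φ(10 / (20 × √(2/n)) − 1.960):

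| x (assumed) | n per arm | lost per arm | power |
|---|---|---|---|
| 0% | 62.1 | 0 | 79.6% |
| 2% | 60.9 | 1.2 | 78.8% |
| 5% | 59.0 | 3.1 | 77.5% |
| 10% | 55.9 | 6.2 | 75.3% |
| 15% | 52.8 | 9.3 | 72.9% |
| 20% | 49.7 | 12.4 | 70.3% |

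For x of 5–10% the fall is 79.6 − 77.5 = 2.1 to 79.6 − 75.3 = 4.3 percentage points. The t distribution gives 78.9%, 76.8% and 74.5% for x of 0%, 5% and 10%, so nearly the same falls.

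**4. Size of a possible bias.** Suppose 10% of one arm only are deleted, scores are normal with SD 20, and the baseline-to-3-month correlation is 0.6 (all assumed). The mean of the worse half lies 20 × √(2/π) = 15.96 points above the overall mean.

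- *Deletion related to the baseline score*, which is already recorded when the 1-month visit is missed. If all deleted participants come from the worse half at baseline, the arm's 3-month mean shifts by 0.6 × 15.96 × 0.1/0.9 = 1.06 points. If three quarters do, the shift is half that, 0.53. Adjusting for baseline removes essentially all of it.
- *Deletion related to the 3-month score itself.* The 3-month mean shifts by 15.96 × 0.1/0.9 = 1.77 points, or 0.89 if three quarters come from the worse half. The shift in change from baseline is (1 − 0.6) times these, 0.71 or 0.35 points.

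The largest of these, 1.77, is 18% of the 10-point target. It needs one-sided missingness driven by an outcome measured after the missed visit.

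**5. Which listed tests lose the 3-month score?** Repeated-measures ANOVA and Friedman's test over three visits do. The group t-test and rank-sum test at 3 months do not. Nor do the paired t-test and signed-rank test of baseline against 3 months.

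**The case against.** Four points on the other side have force.

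*A reader might infer that 13.1.3 contradicts 13.3.* The text does not go that far. The visit-level sentence most naturally concerns observations missing within an attended visit, such as a lost tear measurement. The sentence before it lets a missing value be left out of analyses of that same variable, so dropping an incomplete OSDI series from one OSDI test is compatible with its letter. What remains is a tension with the available-case intent, and a missing rule for missed visits.

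*A reader might infer that 3-month scores will be lost.* That is not established. The parametric list is permissive, ANOVA follows an "or", and Friedman's test is offered beside the signed-rank test. The loss occurs only if one of the two complete-row tests is chosen. The plan does not rule that choice out, and among the tests listed for scores these two are the ones that take all three visits together.

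*A reader might infer that the trial falls below its planned power because of this.* The power figures above belong to a two-sample comparison at 3 months, which would itself delete nobody; they only translate lost participants into a familiar scale. With an assumed correlation of 0.6, a contrast in change from baseline has SD 20 × √(2 × 0.4) = 17.9 and power of about 87%, 85% and 83% at 62, 59 and 56 per arm, still above 80%. The 62.1 per arm left after drop-out also gives slightly under 80% before any deletion.

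*The two tests are described for within-subject differences, not for comparing arms.* This is correct. It means the plan's longitudinal methods neither keep all the data nor deliver the between-arm contrast the trial is about, which supports replacing them.

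**Conclusion.** The point holds in conditional form. If repeated-measures ANOVA or Friedman's test is applied over the three visits, a participant missing only the 1-month visit is deleted and an observed 3-month score is discarded, against the intent of 13.3. With an assumed 5–10% of such participants, the loss is about 3–6 per arm, worth roughly 2–4 percentage points of power on the sample-size calculation's own comparison. The documents give no missed-visit rate, so the true figure could lie outside that range.

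Bias cannot be sized from the documents. In the scenarios tried it is between 0.35 and 1.8 OSDI points, small against the target of 10, and close to zero after baseline adjustment when missingness depends on the baseline score.

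This is a moderate weakness, worth correcting because a better method costs little. It does not threaten the trial's validity.

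**What to change.** In section 13.1.3, replace repeated-measures ANOVA for the interval-scale symptom scores with a linear mixed model for repeated measures. Terms: arm, visit, arm × visit and baseline score, with unstructured covariance, using all observed scheduled follow-up scores. Name the 3-month between-arm contrast as the efficacy test. A participant who missed the 1-month visit then keeps the 3-month score, and one who left after 1 month still contributes that score. The model relies on missingness being explained by the observed scores and the model's terms; the plan should say so.

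For any score analysed as ranked, use a between-arm rank-sum comparison at 3 months in place of Friedman's test.

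In section 13.3, add one sentence stating that missing a visit does not remove a participant's other visits from the efficacy analysis.

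The cost is revised SAP wording and slightly more analysis work. The model can be fitted in SPSS, the named software, and no new data are needed. The change should be made before unmasking.

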**Table 4**

Procedures/ Data (Y/N)	Visit 1	Visit 2	Visit 3/Study Exit	Unscheduled / Adverse Events
	BL	(1M from BL)	(3M from BL)	
Visit Window	N/A	$\pm$ 7 days	$\pm$ 14 days	N/A
Informed Consent	Y	N	N	N
Meet Inclusion/Exclusion Criteria	Y	N	N	N
Ocular and Medical History, Medications, Demographics	Y	N	N	N
Updated History, Symptoms and Problems	N	Y	Y	Y
Vision Tests (Visual Acuity)	Y	Y	Y	Y
Symptom Survey	Y	Y	Y	*
Nutrition Questionnaire	Y	N	Y	N
Comfort Questionnaires	Y	Y	Y	*
Health and Wellbeing Questionnaire	N	Y	Y	*
Body Mass Index and Body Fat Composition	Y	N	N	N
Tear Film Evaluation	Y	Y	Y	*
Slit-Lamp Biomicroscopy: Anterior ocular health including evaluation of cornea & conjunctiva	Y	Y	Y	Y
Dispense Study Product	Y	Y	N	N
Return Unused Study Product	N	Y	Y	*
Adverse Event Data	(Y)**	(Y)**	(Y)**	Y

Y = Yes, required information, N = No, not required

\* At optometrists discretion

\*\* If adverse event detected at time of visit

M = Month

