## **7.3. Withdrawal and Follow-up Procedure**

Participants who are permanently withdrawn from the study should be seen as soon as possible after stopping use of the study product for a final visit to assess participant safety and to return any unused study product. This may be done at a routine clinic visit or an unscheduled visit if it occurs between routinely scheduled visits.

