### 7.3.1. The Final Study Exit Visit

Where possible, the data requirements for the final study exit visit are the same assessments as for the 3 month visit shown in Table 5. However, the minimum data requirements include:

- Visual acuity
- Slit-lamp biomicroscopy (ocular redness, corneal and conjunctival staining)

For withdrawal of consent, a 'Revocation of Consent' document should also be signed, if possible.

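### For participants permanently withdrawn before 3 months, the documents conflict on the primary questionnaires at exit, no 3-month score is sought, and no missing-data sensitivity analysis is planned

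*Combined protocol and SAP*

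**What the plan says.** The synopsis makes OSDI, OCI and DEQ-5 the primary efficacy variable, and Section 6.1.4 sets visits at baseline, 1 month and 3 months. For someone permanently withdrawn in between, the relevant text is spread over five places.

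- **Section 7.3**: such participants "should be seen as soon as possible after stopping use of the study product for a final visit to assess participant safety" and to return product. It adds: "This may be done at a routine clinic visit or an unscheduled visit if it occurs between routinely scheduled visits".
- **Section 7.3.1**: as far as can be achieved, "the data requirements for the final study exit visit are the same assessments as for the 3 month visit shown in Table 5". The stated minimum is visual acuity and slit-lamp findings, with no questionnaire. Table 5 lists only visit names; the assessments are in Table 4.
- **Table 4**: one column is headed "Visit 3/Study Exit", and the comfort questionnaires (which I take to cover OSDI, OCI and DEQ-5) are marked Y, defined in the key as required. In the unscheduled-visit column they are left to choice: "At optometrists discretion".
- **Section 13.1.3**: "The analysis of efficacy variables such as subjective ratings will employ only scheduled and evaluable visits". Evaluable is not defined.
- **Section 13.3**: "Data from unscheduled visits will be used only for adverse response analysis", and "Individual data points that are missing will be excluded from analysis involving only those specific variables".

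No section asks for a questionnaire at 3 months after permanent withdrawal. Contact under Section 7.3.2 seeks the reason, safety status and concomitant therapies; follow-up under Sections 7.3.3 and 12.5 concerns adverse events. The only with-and-without comparison in Section 13.3 is for outliers.

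**The concern.** Section 13.1.3 puts everyone who started treatment in the analysis dataset, but a participant with no 3-month score adds nothing to a 3-month comparison. The withdrawal reasons in Section 7.2 include uncorrectable trial-related symptoms, serious adverse events and non-compliance, all of which could be related to symptoms or to arm. If so, those who remain at 3 months are a selected group, and the supplement-placebo difference is distorted.

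The plan neither limits this, since it collects nothing later, nor displays it, since it has no sensitivity analysis. Two analysts working from Table 4 and from Sections 7.3 and 13.3 could also handle the same exit score differently.

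The point concerns permanent withdrawal only. Section 4.2.1 can be read as allowing a temporary stop.

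**Working it through.** **1. The plan's own figure.** Inputs from Sections 13.1.1 and 13.1.2: difference 10, SD 20, two-sided 5%, power 80%, 10% dropout. Per arm, n = 2 × (1.96 + 0.84)² × 20² / 10² = 62.8, so 63. Then 63 × 1.10 = 69.3, giving 69 per arm and 138 in total, as stated. (Dividing by 0.90 gives 70 per arm, 140 in total.) Power is 83.6% with 69 per arm and 79.6% with 69 × 0.90 = 62.1. The allowance covers the precision lost to 10% dropout. It does nothing about bias.

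**2. Two readings of one exit score.** With 1 month taken as 30 days, the windows are days 23–37 (30 ± 7) and 76–104 (90 ± 14). Take someone who leaves and attends an exit visit on days 38–75.
- By Table 4 this is the Study Exit column: questionnaires are required, and the score might be entered as Visit 3.
- By Sections 7.3 and 7.3.1 it is an unscheduled visit with no questionnaire in the minimum. By Sections 13.1.3 and 13.3 any score taken stays out of efficacy.

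On both readings nothing is sought at 3 months.

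**3. How many.** 138 × 10% = 13.8, so up to about 14 participants lack a 3-month score. Of days 1–75, 15 fall in the 1-month window and 60 (80%) do not. Assuming even timing and that every leaver attends, 13.8 × 0.80 = 11.0 have an off-window exit score; if half attend, 5.5. The documents do not split the 10% by cause.

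**4. Bias.** Let d be the dropout share in an arm and g the amount by which leavers' 3-month OSDI would be worse than completers'. The completer mean is below the full-arm mean by d × g, so the difference between arms is off by d₁g₁ − d₂g₂. Type I error uses SE = 20 × √(1/n₁ + 1/n₂), with n = 69 × (1 − d). The values g = 10 and 20 are assumed.

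| Scenario | SE | Bias, points | Type I error |
|---|---|---|---|
| Equal dropout, equal gaps | – | 0 | 5% |
| 11.5% v 8.5%, same gap | 3.590 | 0.3–0.6 | 5.1–5.3% |
| 12.5% v 7.5%, same gap | 3.591 | 0.5–1 | 5.2–5.9% |
| 15% v 5%, same gap | 3.595 | 1–2 | 5.9–8.6% |
| 10% in each arm, gap in one arm only | 3.589 | 1–2 | 5.9–8.6% |

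The second row takes the GI risks in Section 12.4.1 (below 2% and below 1%, together 3 percentage points) as the only source of extra dropout. The other splits are assumed. Example for the last row: 10% × 20 = 2 points; 2 / 3.589 = 0.557; Φ(−1.96 + 0.557) + Φ(−1.96 − 0.557) = 0.080 + 0.006 = 8.6%.

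**5. What modelling alone can do.** I simulated leavers after the 1-month visit (bivariate normal, 2,000,000 draws, 15% dropout, assumed correlation 0.5–0.7 between 1- and 3-month scores). A model using the 1-month score removes about all the bias if leaving depends on that score. It removes only 17.5–47.9% if leaving depends on the unseen 3-month score. Later collection therefore matters more than the model.

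**The case against.** The strongest reply is that the plan does ask for the questionnaires at exit: Table 4 marks them required, and Section 7.3.1 treats its minimum as a floor beneath the full 3-month set. That stands. A reader might infer that the plan simply omits them; the documents do not support this. What they show is a conflict between Table 4 and Sections 7.3, 7.3.1 and 13.3.

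A reader might also infer that the 3-month comparison includes only in-window scores. That does not follow either: if Study Exit counts as Visit 3, an early score might enter, and no passage expressly bars out-of-window scores. Nor is it assured that later leavers' 1-month scores are always used, because Section 13.1.3 also permits repeated measures ANOVA without saying how it treats a participant missing one visit.

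The size is open to challenge too. The one scenario tied to figures in the documents gives 0.3–0.6 points, which is negligible, and it assumes that every GI event leads to dropout and none occurs on placebo. The 15% v 5% split is invented, and a 20-point gap is a full planning SD. This stands as a limit on what can be claimed. The same-gap scenarios are not an upper bound, however: equal 10% dropout with a gap in one arm only already gives 1–2 points.

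Finally, a person who is leaving cannot be compelled to fill in forms, and the Table 5 reference is clerical. Both are true. Neither supplies a 3-month score or a sensitivity analysis.

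**Conclusion.** The concern holds as a conflict and a gap. The documents disagree on whether the primary questionnaires are required at exit and on whether an early-exit score counts. Under any reading, no 3-month score is sought after permanent withdrawal, missing points are excluded, and no missing-data sensitivity analysis is given.

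The bias is unknown and is zero if dropout and gaps match between arms. The illustrations reach 2 points, or 20% of the 10-point design difference. They rest on assumed gaps of 10–20 points and, GI scenario aside, on assumed dropout patterns. They are neither estimates nor bounds.

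A reader might go further and infer that the 3-month result will be biased or the trial invalid. Nothing in the documents shows that: they give no withdrawal by arm and no outcomes for leavers, and the sample size reproduces on its own inputs. The plan should be amended because the remedy is cheap and the uncertainty would otherwise stay hidden.

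**What to change.** 1. **Exit visit.** Reconcile Table 4 with Sections 7.3, 7.3.1 and 13.3. List OSDI, OCI and DEQ-5 in the exit minimum, correct the table reference, and state that an exit score counts for a visit only if it falls in that visit's window.
2. **Later scores.** State in Sections 7.2 and 7.3 that the 1- and 3-month questionnaires are still sought after product is permanently stopped, unless consent is withdrawn. Align Section 13.2, which ends the trial with the last active participant and does not count discontinued participants as active.
3. **Analysis.** In Sections 13.1.3 and 13.3, compare arms as allocated, for each of OSDI, OCI and DEQ-5, with a mixed model using all in-window post-baseline scores. Add a sensitivity analysis that imputes missing 3-month scores and shifts them in coded arm A, then in coded arm B: by 10 and 20 points for OSDI, with shifts suited to the scale for OCI and DEQ-5. Shifting each arm in turn keeps the masking, since Section 6.1.2 holds the code until after data analysis. With 10% missing, the OSDI shifts move the result by 1–2 points (0.10 × 10 and 0.10 × 20).

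**Cost.** Short paper forms at a visit already planned, some extra participant contact, more analysis work, and slight dilution from scores taken off product. Participants who are lost to follow-up or withdraw consent remain missing.

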### **5.2. Clinical Hypothesis**

A greater reduction in ocular discomfort and/or signs of dry eye will be observed after daily consumption of the supplement nutraceutical formulation (combination of flaxseed oil, borage oil and fish oil omega-3 fatty acids) over a 3 month period compared to a placebo control.

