## 6. STUDY DESIGN

This study will be a prospective, randomised, placebo-controlled, double masked study conducted over a 3-month period.

One hundred and thirty-eight (138) participants who meet the inclusion / exclusion criteria and give informed consent will be randomised to either the test capsules containing a combination of flaxseed oil, borage oil and fish oil omega-3 fatty acids ("supplement") or placebo capsules, identical in appearance, containing non-active ingredients polyethylene glycol (500mg), oleic acid (659mg) and propylene glycol (115mg) to be taken by mouth three times daily for 40 days and then two times daily for the remainder of the study, as per the manufacturer's guidelines. Every effort will be made to stratify enrolment by disease severity to ensure participants with mild, moderate and severe dry eye are represented in the study population. Stratification will be in a 2:2:1 fashion i.e. OSDI score >12 (55 participants), OSDI score >20 (55 participants) and OSDI score >45 (28 participants). Participants will be stratified according to dry eye severity prior to randomisation.

There will be a total of 3 scheduled study visits over a period of approximately 3 months - Day 1, 1 month and 3 months. Ocular comfort and symptoms of dry eye will be assessed via questionnaires. The tear film and ocular surface will be assessed using specialised instruments (slit lamp biomicroscopy, Lipiview, Vapometer and Oculus Keratograph) and stains. Safety will be assessed through measurement of visual acuity, ocular redness (eyelid and bulbar conjunctival redness), evaluation of the ocular surface using the slit lamp biomicroscope and the administration of a questionnaire to assess general health and wellbeing.

In addition, at the first visit only, body mass index and body fat composition will be measured to investigate the potential relationship between nutrition, body composition, and dry eye (Ho et al, Eye Contact Lens; Epub ahead of print 27 May 2016).

All proposed procedures conform to the NHMRC Statement on Human Experimentation.

Participants are considered enrolled when they have signed the informed consent form and are regarded as part of the clinical trial population.

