### 6.1.2. Randomisation and Masking

Prior to initiation of study treatment, each subject who provides informed consent will be assigned to a subject number that will serve as the subject identification number on all study documents. Subject numbers will be assigned in ascending order and should not be omitted or reused.

Eligible subjects will be stratified according to dry eye severity (mild, moderate or severe) and then randomly assigned to 1 of the 2 study treatments. A randomization scheme will be prepared in advance.

Test and placebo capsules will be manufactured in accordance with local regulations including the TGA guidelines. All capsules will be identical in appearance as the outer capsule will be the same as the commercial test product. The manufacturer will code, bottle and label the test and placebo capsules to ensure that participants and investigators will be masked throughout the study duration. Both test and placebo capsules will have the same outer packaging and will be labelled as capsule "A" or "B". The code will be broken after completion of the study and data analysis, or if required for participant safety.

The recommended dosage will be 3 capsules per day by mouth to be taken with a meal for 40 days, and then 2 capsules per day thereafter for approximately 50 days, as per the manufacturer's guidelines.

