#### 13.1.2. Significance

A p-value less than or equal to 5% will be considered to be statistically significant.

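### Section 13.3 lets the change in the test result decide whether outliers stay in, with no outlier definition, threshold or duty to report both analyses, so the 5% level is not assured

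*Combined protocol and SAP*

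**What the plan says.** Two sentences in Section 13.3 (Accountability of Data) govern outliers. The first sets the criterion: "Inclusion of outliers in the analysis will be based on the magnitude of change in test statistic with and without the outliers". The second sets a default and an exception: "Outliers will preferably be retained unless there is significant change in test results".

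The related text elsewhere is short:

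- Section 13.1 offers data checks but no exclusion rule: "Data will be investigated for quality using range checks and frequency distribution".
- Section 13.1.2 sets the level: "A p-value less than or equal to 5% will be considered to be statistically significant".
- Section 13.1.3 leaves the test open: "Commonly used tests of significance at each visit may include paired t-tests and group t-test for parametric data". It also lists rank tests and repeated-measures ANOVA, and applies Bonferroni's correction to multiple comparisons.
- Section 6.1.2 labels the capsules A or B and keeps the allocation masked during analysis: "The code will be broken after completion of the study and data analysis, or if required for participant safety".

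No section defines an outlier, says whether outliers are identified within each arm or on the pooled data, sets a threshold for the exception, or requires both analyses to be reported.

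**The concern.** An outlier rule should turn on whether a value is an error, or on a definition fixed in advance. This one turns on what the value does to the comparison under test, so the result helps to choose its own data set.

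The default of retention gives little protection. Suppose the exception means that the significance verdict changes. When the full and trimmed analyses agree, the choice between them does not matter. When they disagree, the trimmed one stands. The reported verdict is then always the trimmed verdict, and the default has no effect in the cases where it would count.

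Masking does not remove the problem. With groups coded A and B the analyst cannot easily steer towards the supplement, but the A-versus-B statistic and its p-value are visible, and Section 13.3 requires the analyst to look at them. Bonferroni's correction, as written, does not cover the choice between two versions of the same analysis.

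At stake are the stated 5% level and the reader's ability to see which participants were dropped and what the full data showed. Section 13.3 is not limited to one outcome, so it reaches the primary questionnaires and the tear-film secondary endpoints alike.

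**Working it through.** **The plan's own figure.** Section 13.1.1 gives a difference of 10, SD 20, two-sided 5% and 80% power.

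n per arm = 2 × (1.960 + 0.842)² × 20² / 10² = 62.8, rounded up to 63. Allowing for 10% drop-out, 63 / 0.9 = 70. The stated 69 per arm (138 in total) is reproduced to within one participant per arm. Evaluable participants: 69 × 0.9 = 62 per arm, the size used below.

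**Set-up.** Trials were simulated with no treatment effect and tested two-sided at 0.05. The plan supplies no outlier definition, threshold, final test or distribution, so these are assumptions:

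- Outlier definitions: 1.5 × IQR, 2 SD or 3 SD, applied within each arm or on pooled data.
- Verdict changes: the trimmed analysis stands if it gives the opposite verdict.
- Change in t: the trimmed analysis replaces the full one if |t trimmed − t full| exceeds 0.25, 0.5 or 1.0.
- Towards significance only: either analysis may count.
- OSDI change score, chosen because the hypothesis in Section 5.2 is about a reduction ("A greater reduction in ocular discomfort and/or signs of dry eye will be observed after daily consumption"). Section 6 states "Participants will be stratified according to dry eye severity prior to randomisation", so strata were held at 25/25/12 per arm. Baseline was uniform on 12–20, 20–45 and 45–80, mean fall 8 with SD 12, and the month-3 score was clipped to 0–100. This gives a month-3 SD of 20.5 (plan: 20) and a change SD of 10.9.

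The t-test settings used 40,000 trials each (Monte Carlo SE about 0.1 point at 5%) and the rank-sum settings 8,000 (SE about 0.24 point).

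**False-positive rate, t-test on OSDI change score**

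| Use of the rule | Per-arm identification | Pooled identification |
|---|---|---|
| All data kept | 4.9% | 4.9% |
| Verdict changes | 7.5% (IQR), 10.7% (2 SD), 5.5% (3 SD) | 4.9–5.1% |
| Change in t | 4.9–10.5% | 4.9–5.3% |
| Towards significance only | 5.8–11.4% | 5.4–7.3% |

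Per-arm identification flagged on average 1.6 (IQR), 5.6 (2 SD) and 0.3 (3 SD) of the 124 values. The full and trimmed analyses gave opposite verdicts in about 1% (3 SD) to 7% (2 SD, per arm) of trials. With strata drawn at random instead of balanced, the per-arm verdict-change rates were 7.5%, 10.5% and 5.6%, so the result does not rest on exact balance.

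**Other distributions and the rank-sum test**

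| Setting | All kept | Verdict changes, per arm / pooled | Change in t, per arm / pooled | Towards significance, per arm / pooled |
|---|---|---|---|---|
| t-test; normal, t (4 df), lognormal (sigma 0.6) | 4.8–4.9% | 5.3–14.8% / 4.8–5.1% | 4.9–14.8% / 4.8–5.6% | 5.5–16% / 5.3–8.0% |
| Rank-sum; change score and the same three | 4.6–5.1% | 4.9–9.3% / 4.6–5.1% | not run | 5.0–10.0% / 4.9–6.9% |

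**Raw month-3 OSDI, unadjusted t-test, balanced strata.** All kept 0.14%; verdict changes 0.3–2.0% per arm and 0.2–0.7% pooled; towards significance only, at most 2.0%. The low starting rate arises because the strata are balanced by design but the test ignores them. It is no merit of the outlier rule.

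**Reading the pattern.** Trimming each arm around its own centre shrinks the estimated SD by more than it steadies the means, so t is too large too often. Flags set on pooled data ignore the arm labels, and a trimmed test that always stands then keeps close to 5%. The plan does not say which applies.

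**The case against.** The strongest reply is that the inflation comes from assumptions added to the plan. Section 13.3 does not say outliers are identified per arm, and pooled identification used mechanically stays near 5%. That is right. It limits the claim to the level not being assured and rules out quoting any one expected error rate.

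The variable is also a choice. The plan is powered on an OSDI difference with SD 20, and Section 13.1.3 does not name a change score. For raw month-3 scores no rate above 5% is claimed. This stands too, although the plan does not commit to raw month-3 scores either.

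The highest figures need settings unlike a bounded score: 14.8% and 16% come from lognormal data with per-arm identification, and 10.7% needs a 2 SD cut-off. At 3 SD the change score gives only 5.5%. The rates for use towards significance only describe misuse, since Section 13.3 looks at the size of the change and not its direction. The wording does not prevent that use, but those rates are not the plan's operating characteristics.

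Finally, Bonferroni's correction and repeated-measures ANOVA were not simulated, and the quality checks in Section 13.1 may catch plain errors. These points limit the figures. They do not supply a definition, a threshold or a reporting duty.

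**Conclusion.** The concern holds. Section 13.3 states a rule under which the result of a comparison decides the data that enter it, and nothing elsewhere in the plan constrains that rule. The 5% level cannot be verified from the document.

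The size depends on what the plan leaves open. For a t-test on the OSDI change score with 62 per arm, the error is about 5% if outliers are identified on pooled data and the rule is applied mechanically. It is 5.5% to 10.7% if they are identified per arm and the trimmed verdict stands. These figures rest on the assumed outlier definitions, the OSDI model and a single unadjusted comparison. Confidence is high in the defect of wording, and lower in any particular inflation figure. It should be fixed. It is not more serious than that, because retention is the stated default and the harm is conditional.

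**What to change.** Replace the two outlier sentences in Section 13.3 with text along these lines:

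> All valid observations are retained in the primary analysis. A value is corrected or excluded only for a documented measurement or transcription error, decided before any A-versus-B comparison is run and without reference to any test result. A sensitivity analysis that excludes outliers identified on pooled data by a pre-stated definition (or a rank-based or robust analysis) is reported alongside, whatever its result.

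The outlier definition should be written into the plan at the same time. Keeping all data removes the dependence on the result: it gave 4.9% for the change-score t-test and 4.6% to 5.1% across the other distributions and the rank-sum test. The cost is a wording change and one extra sensitivity analysis. No participants or additional data are needed, and the sample size of 138 is unaffected.
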